1 INTRODUCTION

The JET Enhanced Thrombectomy intervention (JETi) Hong Kong Post Market Study (PMS) is a post-market study designed to collect real-world data on the safety, performance, and clinical benefits of the JETi™ Hydrodynamic Thrombectomy System (HTS) (will be refer to as JETi System throughout this document) for the treatment of acute/subacute thrombosis in the peripheral vasculature.

The JETi System is a hydro-mechanical aspiration system manufactured by Abbott Medical, consisting of a catheter, pump set, and accessories. The system is intended to remove/aspirate fluid and break-up soft emboli and thrombus from the peripheral vasculature and to subselectively infuse/deliver diagnostics or therapeutics with or without vessel occlusion.

Several published studies have shown that the JETi System is safe and effective in the peripheral vasculature. In a retrospective study¹ of 18 consecutive patients with thrombus in the iliofemoral, axillosubclavian, and portal veins, mean thrombus reduction with JETi alone was 92%. Procedural success was 100%, and technical success with the JETi alone was 76%; 24% of procedures requiring subsequent catheter directed thrombolytics (CDT) overnight. One subsegmental pulmonary embolism (PE) event was reported. In another study, 30 patients with acute lower extremity deep vein thrombosis (DVT), including iliocaval, iliofemoral, and femoropopliteal) were treated with the JETi System.²

Technical success was 93.3%, and mean thrombus removal was 74.0%. No major complications were observed. In a prospective pilot study conducted in 47 patients with thrombus in the iliocaval or iliofemoral veins treated in a single session with the JETi System, unobstructed flow was reestablished in 87% of patients with no major adverse events through 30 days.³ In addition to these studies reporting on venous thromboses, a recent presentation by Dandu et al.⁴ reported on a retrospective review of 27 patients treated for acute lower extremity ischemia. The success rate of all interventions in which the JETi System was used was 85%.

The JETi Hong Kong PMS is a single-arm, multi-center study registering approximately 20 subjects from up to 5 sites in Hong Kong. Both prospective and retrospective consent (if all assessments needed for primary endpoints are complete) are permitted. In cases of prospective consent, subject participation will be up to 30 days. If consent occurs after the procedure, duration of participation may vary given timing of consent but will not exceed 30 days.

This study will collect data on how the JETi System performs in the treatment of patients undergoing a percutaneous thrombectomy procedure for peripheral thrombosis. Subjects treated for arterial, venous, or arteriovenous thromboses, and subject with diagnoses such as acute limb ischemia (ALI), chronic limb ischemia/chronic limb threatening ischemia (CLI/CTLI), peripheral artery disease (PAD), deep vein thrombosis (DVT), hemodialysis access thrombosis, and others may be included. The details of data to

¹ Cournoyer-Rodrigue J, Bui TB, Gilbert P, et al. Percutaneous Thrombectomy with the JETi8 Peripheral Thrombectomy System for the Treatment of Deep Vein Thrombosis. *J Vasc Interv Radiol.* 2020;31(3):444-453.e2. doi:10.1016/j.jvir.2019.10.022

² Khalsa B., Luu K., Gilbert B., et al. Single-session treatment of lower extremity venous thrombosis using a novel thrombectomy device: results of a pilot study. *J Vasc Interv Radiol.* 2020; 31(3):S83. doi:10.1016/j.jvir.2019.12.217

³ Razavi C, Khalsa B, Openshaw L, Razavi MK. Single-Session Treatment of Patients with Symptomatic Iliocaval and Iliofemoral Deep Vein Thrombosis: Technical Results of a Prospective Pilot Study. *J Vasc Interv Radiol.* 2022;33(2):183-188. doi:10.1016/j.jvir.2021.10.011

⁴ Dandu C, Natour A, Onofrey K, et al. Single-Center Experience with JETi Aspiration Thrombectomy for Acute and Subacute Lower Limb Ischemia. Presented at the Vascular Annual Meeting (VAM), June 2022.

be collected and the timepoints for the purpose of this study are described in this plan. Each participating investigator will determine and implement the best treatment strategy for their patients based on the clinical situation and local physician practices. This study will be conducted in accordance with this CIP. All investigators involved in the conduct of the study will be qualified by education, training, and experience to perform their tasks and this training will be documented appropriately.

2 CLINICAL INVESTIGATION OVERVIEW

2.1 Clinical Investigation Objective

The objective of the JETi Hong Kong PMS is to collect real-world data on the safety, performance, and clinical benefits of the JETi System for the treatment of thrombosis in the peripheral vasculature.

2.2 Device Used in the Clinical Investigation

2.2.1 JETi Hydrodynamic Thrombectomy System

This post market study includes commercially available JETi Hydrodynamic Thrombectomy System at participating sites.

2.2.2 Indication for Use

The JETi Hydrodynamic Thrombectomy System is intended to remove/aspirate fluid and break-up soft emboli and thrombus from the peripheral vasculature and to subselectively infuse/deliver diagnostics or therapeutics with or without vessel occlusion.

2.2.3 Description of the Device

The JETi Hydrodynamic Thrombectomy System is a hydro-mechanical aspiration system intended for the removal of intravascular thrombus. The system is comprised of the JETi Catheter, JETi Pump Set, and JETi Saline Drive Unit (SDU), accessory cart, suction tubing, and non-sterile canister set. The JETi System is designed to simultaneously deliver a stream of high-pressure saline via a displacement pump to the distal tip of the JETi Catheter, while aspirating thrombotic material macerated by the saline stream. A thorough understanding of each component in the JETi System is required for proper operation. Please refer to the electronic Instructions for Use (eIFU) before attempting to use any part of the JETi System.

3 CLINICAL INVESTIGATION DESIGN

The JETi Hong Kong PMS is a single-arm, multicenter study to collect real-world data on the safety, performance, and clinical benefits of the JETi System for the treatment of acute and subacute thrombosis in the peripheral vasculature. This is a post-market study that will register approximately 20 subjects at approximately 5 centers in Hong Kong. Both prospective and retrospective consent (if all assessments needed for the primary endpoints are complete) are permitted. Subjects participating in this study will be followed for up to 30 days

[REDACTED]
After index procedure, subjects will be evaluated at discharge
and 30 days in cases of prospective consent.
[REDACTED]

The Sponsor has designed this study to involve as little pain, discomfort, fear, and any other foreseeable risks as possible for subjects. Refer to the Risks Analysis section (**Section 15.0**) of this clinical investigation plan for details.

[figure not shown]
3.1 Clinical Investigation Procedures and Follow-up Schedule

The study flowchart is shown in **Figure 1**, and the follow-up requirements are described in this section. After meeting all eligibility criteria, a subject is considered enrolled in the study from the moment the subject provides written informed consent. The point of registration in the study is when a JETi Catheter is introduced into the intended vasculature of an enrolled subject during the procedure (Day 0).

A subject who is enrolled but not registered in this study will be considered a screen failure. Consenting after the JETi procedure is deemed acceptable if all assessments needed for primary endpoints were completed at baseline. In the cases of retrospective consent, the point of registration will be the same and any procedural information would be entered post-consent and defined adverse events (AEs) will be collected retrospectively from the point of registration. All registered subjects will be followed for up to 30 days in cases of prospective consent and will vary for retrospective consent. Registered subjects will be evaluated, and data will be collected at baseline, procedure, discharge, and at 30 days after Day 0.

[figure not shown]
Figure 1: Study Flowchart

a) Prospective consent

* ≠ procedure performed in the treatment of patients undergoing a percutaneous thrombectomy procedure for peripheral arterial, venous, and arteriovenous thrombosis

b) Retrospective consent*

* procedure performed in the treatment of patients undergoing a percutaneous thrombectomy procedure for peripheral arterial, venous, and arteriovenous thrombosis

*Consenting after the index procedure is acceptable if all assessments needed for primary endpoints are complete

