4.1 Primary Endpoints

4.1.1 Arterial and Arteriovenous Subjects

For subjects treated for arterial thrombosis (may include diagnoses such as acute limb ischemia, chronic limb ischemia/chronic limb threatening ischemia, peripheral artery disease, etc.) or arteriovenous (AV graft, AV fistula) thrombosis, all endpoints are descriptive.

For subjects treated for arterial or arteriovenous thrombosis, the primary endpoints are:

- **Clot removal grade** for each JETi-treated target vessel from pre-JETi angiogram to post-JETi angiogram (post-JETi thrombectomy and prior to any adjunctive therapies to treat underlying culprit lesions) per the grades in **Table 1** (vessel basis). The independent imaging core laboratory will be responsible for assessing this endpoint.
- **Composite of JETi-related major adverse events** (MAEs) up to 30 days post-JETi procedure, defined as the following JETi-related events adjudicated by a clinical events committee (CEC) (subject basis) death, major amputation of the treated limb, or major bleeding. Refer to **Appendix II** for definitions of major adverse events.

Table 1. Clot Removal Grade

Grade I	< 50% reduction
Grade II	50- <95% reduction
Grade III	95 - 100% reduction

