8 STATISTICAL CONSIDERATIONS

8.1 Analysis Populations

All registered subjects will be included in the analysis.

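### The plan contradicts itself on whether retrospectively consented subjects are evaluated at day 30, and no rule says when their 30-day MAE status is missing

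*Combined protocol and SAP*

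**What the plan says.** Subjects may consent before or after the procedure. On what follows, the readable text falls into two groups.

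**Text that limits day 30 or leaves it open after retrospective consent**
- Section 3 has subjects evaluated after the procedure at discharge "and 30 days in cases of prospective consent".
- Section 3.1: "All registered subjects will be followed for up to 30 days in cases of prospective consent and will vary for retrospective consent".
- Section 1: "If consent occurs after the procedure, duration of participation may vary given timing of consent but will not exceed 30 days". This sets a maximum and no minimum.
- Section 5.8 gives 30 days as the expected participation for prospective consent. It lets subjects exit either at the 30-day visit or once 30 days have passed since the procedure.

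**Text that applies day 30 to everyone**
- Section 3.1, in the very next sentence: "Registered subjects will be evaluated, and data will be collected at baseline, procedure, discharge, and at 30 days after Day 0".
- Section 7.3.1 has adverse events reported for each subject up to the 30-day visit.
- Section 8.4 holds the analysis until all registered subjects have reached that visit.
- Tables 5 and 6 schedule the visit whatever the consent route. Their only exemption for post-procedure consent is the baseline SF-12.

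For the period before consent, section 3.1 says "defined adverse events (AEs) will be collected retrospectively from the point of registration". The MAE composites in 4.1.1 and 4.1.2 run to 30 days after the procedure. On the analysis set, section 8.1 says: "All registered subjects will be included in the analysis". Section 8.8 excludes missing data without saying what missing means for an MAE.

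**The concern.** When a subject consents should affect when participation starts, and not how much of the 30-day safety window is observed. Read literally, section 3 lets a site omit the 30-day evaluation for a subject who consents after the procedure. The sentence in 3.1 that follows the consent split tells the same site to do it. With about 20 subjects at up to five sites, different readings would give a primary safety endpoint with unequal observation behind it.

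The visit matters most for venous subjects. Re-thrombosis of a treated vessel is a component of their composite, and the 30-day duplex scan is the only imaging scheduled after the index procedure that could show it.

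MAEs reach the database as reported events. Without an evaluability rule, a subject followed to day 30 without an event and a subject not followed to day 30 look alike.

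**Working it through.** **1. Is there a conflict?** Section 1 offers a way to reconcile part of the text. If participation is counted from consent to a fixed day 30, its length varies with the consent date while the endpoint stays put. That reading makes the two adjacent sentences of 3.1 compatible. It does not explain section 3, which makes the 30-day evaluation itself conditional on prospective consent. Section 7.3.1 also lets surveillance end when the subject concludes participation, for which section 1 gives no minimum after retrospective consent.

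**2. Which part of the window is at risk?** Look-back collection covers registration to consent. The unprotected part is consent to day 30. For example, with consent on day 10 it is 30 − 10 = 20 days, and with consent on day 25 it is 30 − 25 = 5 days. Later consent therefore leaves less of the window exposed.

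**3. Does the precondition for retrospective consent close the gap?** Section 3.1 says: "Consenting after the JETi procedure is deemed acceptable if all assessments needed for primary endpoints were completed at baseline". A 30-day MAE outcome cannot be complete at baseline. Sections 1, 3 and 5.5 require completeness but give no time point. The gap stays open.

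**4. How would an unobserved subject be handled?** Section 8.1 includes the subject and section 8.8 drops missing values. Nothing says whether an absent day-30 evaluation makes MAE status missing. The plan thus permits two denominators. The table uses N = 20, exact (Clopper-Pearson) 95% limits, and m subjects without a day-30 evaluation. The values of m and the event counts are assumed.

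| Events | m | Counted event-free | Excluded | Unobserved all counted as events |
|---|---|---|---|---|
| 0 | 2 | 0/20, upper limit 16.8% | 0/18, upper limit 18.5% | 2/20 = 10% |
| 0 | 5 | 0/20, upper limit 16.8% | 0/15, upper limit 21.8% | 5/20 = 25% |
| 0 | 10 | 0/20, upper limit 16.8% | 0/10, upper limit 30.8% | 10/20 = 50% |
| 1 | 5 | 1/20 = 5.0% (0.1 to 24.9) | 1/15 = 6.7% (0.2 to 31.9) | 6/20 = 30% |
| 1 | 10 | 1/20 = 5.0% (0.1 to 24.9) | 1/10 = 10.0% (0.3 to 44.5) | 11/20 = 55% |

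The 20 subjects are split between the arterial/arteriovenous and venous composites, so each real denominator is smaller.

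**5. Bias if unobserved subjects are counted event-free.** Let p be the true 30-day rate, s the share not followed to day 30, and f the share of risk captured in those subjects. All three are assumed. The expected observed rate is p × (1 − s + s × f).
- p = 10%, s = 0.25, f = 0.5: 0.10 × (0.75 + 0.125) = 8.75%
- p = 10%, s = 0.5, f = 0.5: 0.10 × (0.5 + 0.25) = 7.5%
- p = 10%, s = 0.5, f = 0.25: 0.10 × (0.5 + 0.125) = 6.25%

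The relative understatement is s × (1 − f). For s from 0.1 to 0.5 and f from 0.25 to 0.75 it runs from 0.1 × 0.25 = 2.5% to 0.5 × 0.75 = 37.5%.

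The plan has no figure of its own to reproduce. It states the sample size without a derivation, and the study is descriptive.

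**The case against.** The best defence is that the plan intends day 30 for everyone. Sections 7.3.1 and 8.4 and both schedules say so, and the tables allow a telephone or virtual contact when an office visit is impossible. Section 5.6 keeps each registered subject in the study until the required follow-up is complete. Section 5.8 counts exit from the procedure. On this view the varying duration is only the time from consent to day 30. This is a fair account of the likely intent, and it rules out reading the plan as a settled exemption for retrospective consent. It does not remove the condition written into section 3.

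Redactions adjoin the relevant text in sections 3 and 5.8, and the retrospective-consent flowchart in Figure 1 is not shown. A clarifying rule may exist there. The readable sentences would still need to agree with it.

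It is also fair that the effect could be small. At a true rate of 10% in 20 subjects, the first two scenarios in step 5 lose 2 − 1.75 = 0.25 and 2 − 1.5 = 0.5 of an expected event. The composite counts only device-related events. Section 1 cites venous series with no major adverse events through 30 days in 47 patients and no major complications in 30.

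A reader might also infer that the shorter observation falls on the sickest patients, because section 5.2.2.1 provides for emergency cases. The same section allows post-procedure enrolment generally, so the documents do not establish that.

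**Conclusion.** The inconsistency is real and bears on a primary endpoint. As readable, section 3 lets a site omit the 30-day evaluation after retrospective consent, against 7.3.1, 8.4 and the schedules. No rule says when 30-day MAE status is missing.

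Three stronger conclusions are tempting but unsupported:
- **Day 30 binds only prospectively consented subjects.** The documents contradict each other on this and do not grant an exemption.
- **Late consenters are the least observed.** Look-back collection makes the opposite true for any given subject.
- **Unobserved subjects will be counted as event-free.** No section says so, and section 8.8 could equally exclude them. The plan leaves the risk open.

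The size of any bias cannot be derived, because the documents give no MAE rate to assume, no expected share of retrospective consent and no event timing. The calculations show direction and scale under assumed inputs only. In a descriptive study without hypothesis tests, this is a correction that should be made because it is cheap. It does not invalidate the design.

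**What to change.** 1. Reconcile sections 1, 3, 3.1 and 5.8 into one rule. Every registered subject, whatever the consent route, has MAE ascertainment from registration through day 30, with record review for the time before consent, and has the 30-day evaluation already in Tables 5 and 6. Only the baseline SF-12 is omitted for post-procedure consent.
2. Correct the condition in 3.1 that primary-endpoint assessments be complete at baseline, and align sections 1, 3 and 5.5 with it.
3. Add to section 8 that a subject is evaluable for 30-day MAE only with an MAE by day 30 or with documented follow-up through the day-30 window.
4. Report the MAE numerator and denominator by consent route beside the pooled result.

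**Cost.** Items 1 to 3 are wording changes, and item 4 adds a short table. Sites that would have skipped the evaluation must arrange a visit or contact for retrospectively consented subjects. The evaluable denominator may be slightly smaller than the number registered.

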3.2 Measures Taken to Avoid and Minimize Bias

An independent core laboratory will be used for imaging data analysis to minimize bias. All angiograms and venograms (pre-JETi, post-JETi, and final) and duplex ultrasound (DUS) images will be sent to the core laboratory for analysis. See **Section 6.3** for details. In addition, a Clinical Events Committee (CEC) will be included for adjudication of safety events.

3.3 Suspension or Early Termination of the Clinical Investigation

The Sponsor reserves the right to discontinue the study at any stage or reduce the follow-up period with suitable written notice to the investigator. Should the Sponsor discontinue the study, sites will follow subjects per routine hospital practice with device-, and procedure-related AEs reported to the Sponsor as per vigilance/commercial reporting requirements. The investigator shall return all study materials to the Sponsor and provide a written statement to the IRB/ EC (if applicable). All applicable study documents shall be subject to the same retention policy as detailed in **Section 11.5** of the CIP.

If the Sponsor suspends or prematurely terminates the study or suspends or prematurely terminates at an individual site in the interest of safety, the Sponsor will inform all other Principal Investigators. If suspension or premature termination occurs, the Principal Investigator or authorized designee will promptly inform the registered subjects at his/her site. A Principal Investigator, IRB/EC, or regulatory authority may also suspend or prematurely terminate participation in the study at the investigational site(s) for which they are responsible. The investigators will follow the requirements specified in the Clinical Trial Agreement.

4 ENDPOINTS

All endpoints are descriptive. There will be no hypothesis testing, and there are no statistical power considerations.

4.1 Primary Endpoints

4.1.1 Arterial and Arteriovenous Subjects

For subjects treated for arterial thrombosis (may include diagnoses such as acute limb ischemia, chronic limb ischemia/chronic limb threatening ischemia, peripheral artery disease, etc.) or arteriovenous (AV graft, AV fistula) thrombosis, all endpoints are descriptive.

For subjects treated for arterial or arteriovenous thrombosis, the primary endpoints are:

- **Clot removal grade** for each JETi-treated target vessel from pre-JETi angiogram to post-JETi angiogram (post-JETi thrombectomy and prior to any adjunctive therapies to treat underlying culprit lesions) per the grades in **Table 1** (vessel basis). The independent imaging core laboratory will be responsible for assessing this endpoint.
- **Composite of JETi-related major adverse events** (MAEs) up to 30 days post-JETi procedure, defined as the following JETi-related events adjudicated by a clinical events committee (CEC) (subject basis) death, major amputation of the treated limb, or major bleeding. Refer to **Appendix II** for definitions of major adverse events.

Table 1. Clot Removal Grade

Grade I	< 50% reduction
Grade II	50- <95% reduction
Grade III	95 - 100% reduction

